6.6.2.2. Sensitivity Analysis

A sensitivity analysis will be performed for the surrogate endpoint using Week 36 results only for patients who would have been expected to complete Week 36 at the time of data cutoff (see [Section 7.7](#) for the definition of this population). Any patient who did not have an assessment at the specified time point for the definition of response will be considered a non-responder (ie, NRI, nonresponder imputation). That is, for the percentage of responders, the patient will be included in the denominator and will not contribute to the numerator. A Cochran-Mantel-Haenszel (CMH) test, adjusting for the 2 randomization stratification factors to compare sparsentan with irbesartan, will be used for this analysis. This sensitivity analysis was the originally planned primary analysis.

As an additional sensitivity analysis for the surrogate endpoint, if a patient is missing a UP/C assessment at a given analysis visit due to only having 1 urine sample available within 5 days, the available single assessment closest to the target day for that visit will be selected for inclusion in analysis for FPPE response using a CMH test. Additionally, a tipping point analysis will also be performed to assess the robustness of the results to the MAR assumption.

For all responder endpoints, an “observed cases” sensitivity analysis will be conducted, excluding those patients who do not provide an assessment at the specified timepoint for the definition of response. That is, for the percentage of responders, the patient will not be included in the numerator or the denominator.

The primary analysis of the surrogate endpoint will use central lab data only. As a sensitivity analysis, local lab data will be included with all observed cases of central lab data and analyzed using the primary model generalized linear model.

6.6.3. Missing Adverse Event or Concomitant Medication Onset Date

Adverse events and concomitant medications with incomplete onset dates will be assumed to have started during the study in accordance with the following prioritized list of assumptions:

1. Missing year: event or medication assumed to have the same year as first dose of study medication or year of end date, whichever is earlier
2. Missing month: event or medication assumed to have started during the study if the year is the same or later than the year of the first dose of study medication. Event or medication assumed to have started at the same month of the first dose of study medication or same month as end date (if year of end date \leq year of event), whichever is earlier
3. Missing day: event or medication assumed to have the same day as first dose of study medication if the year and month of onset are the same as year and month of first dose of study medication or the same day as end date, whichever is earlier. Otherwise, the day is assumed to be the first of the month.

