6.2. Study Design

This is a 112-week, randomized, multicenter, double-blind, parallel, active-control study, with an open-label extension of up to 156 weeks, for a total study duration of up to 268 weeks.

Approximately 300 patients aged 8 to 75 years, inclusive (US and United Kingdom [UK]) and 18 to 75 years, inclusive (countries other than the US and UK), weighing ≥ 20 kg, will be enrolled in the study.

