6.6.4. Missing Adverse Event or Concomitant Medication End Date

If the entire end date is unknown and the event or medication is not considered ongoing at the end of study or follow-up, the event will be assumed to have ended on the last date of contact for the patient.

If only the day of end date is unknown, the day will be assumed to be the last of the month or the last date of contact for the patient, whichever is earlier.

If both the day and month of end date are unknown, the event will be assumed to have ended on the last day of the year or the last date of contact for the patient, whichever is earlier.

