10.1.3. On-Treatment Summaries

Select summaries for TEAEs while on-treatment will additionally be prepared. On-treatment will be defined as TEAEs starting ≤ 30 days from date of last dose in randomized treatment period for patients who discontinue treatment or any TEAE prior to first dose in OLE for patients who complete the randomized treatment period. Summaries will be prepared for TEAEs associated with safety topics of interest in Section 10.1.2. Patient incidence of on-treatment TEAEs and the total number of entries by PT will also be provided.

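### For onset years after the first-dose year, SAP 6.6.3 fills a missing onset month with the calendar month of first dose instead of January, so ongoing or later-ending items can be dated months late

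*SAP*

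**What the plan says.** SAP 6.6.3 lists three assumptions for incomplete onset dates of adverse events and concomitant medications.

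- **Item 2, month missing.** The item is "assumed to have started during the study if the year is the same or later than the year of the first dose" of study medication. The month is then filled in: "Event or medication assumed to have started at the same month of the first dose of study medication or same month as end date". The end-date alternative applies only if the end year is not after the onset year, and the earlier of the two months is taken.
- **Item 3, day missing.** The first-dose day is used only if onset year and month both match first dose, subject to an end-date limit. "Otherwise, the day is assumed to be the first of the month".

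SAP 6.6.4 covers end dates. If the whole end date is unknown and the item is not ongoing, "the event will be assumed to have ended on the last date of contact for the patient".

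The imputed dates are used in several places:

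- **SAP 10.1.3** counts an adverse event as on-treatment if it starts no later than "30 days from date of last dose in randomized treatment period for patients who discontinue treatment".
- **SAP 8.5.2 and 8.7** repeat the eGFR analyses without assessments made after immunosuppressive medication was started or intensified.
- **SAP 8.8.9** analyses days on immunosuppressive agents and time to first use.

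**The concern.** Item 3 distinguishes onsets in the month of first dose from later ones, and gives the later ones the earliest possible day. Item 2 makes no such distinction between years. In the first-dose year, the month and day of first dose are the earliest on-study date, which is the usual conservative choice. In a later year the earliest date is 1 January, yet the rule still gives the month of first dose.

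The end-date cap does not help if the item is ongoing or ends in a later year. Nothing then stops the imputed onset from falling after last contact or death.

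A late date errs in the unwelcome direction for both main uses. An adverse event that began on treatment can be moved past last dose plus 30 days and leave the on-treatment summary. An immunosuppressant start can be moved later, so that eGFR values taken after the true start stay in the analysis meant to exclude them.

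**Working it through.** The plan states no figure for this rule, so there is none to reproduce. I applied item 2 as written.

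**Inputs from the documents.** The month and day rules are from SAP 6.6.3, and the 30-day window is from SAP 10.1.3. The double-blind period is 112 weeks (Protocol 6.2), or 784 days, so onsets can fall in up to two calendar years after the first-dose year. Target days are from SAP Table 2.

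**Assumptions, not in the documents.** First-dose and onset dates are uniform over the calendar and independent. Several item durations were tried.

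**Month count, first calendar year after first dose, no effective cap.** With first dose in month m (1 to 12), the imputed date is late if the true month is before m, with probability (m − 1)/12.

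- January 0/12 = 0%; July 6/12 = 50%; December 11/12 = 91.7%.
- Average: (0 + 1 + … + 11)/144 = 66/144 = 45.8%.
- Mean delay when late: 286/66 = 4.3 months. Late by at least 3 months: 45/144 = 31%.

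**Daily enumeration over 784 days, no effective cap.** Late shares are 0% in the first-dose year, 45.8% in the next calendar year and 72.4% in the one after. That is 56.4% of all later-year items, with a median delay of about 105 days, and 43.3% of all missing-month items.

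**Later-year items when the end-date cap operates where it can:**

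| Duration | Share late | Median delay when late |
|---|---|---|
| Same day | 0% | – |
| 7 days | 13.0% | 4 days |
| 14 days | 25.9% | 8 days |
| 30 days | 55.4% | 16 days |
| 60 days | 56.4% | 42 days |
| 90 days | 56.4% | 68 days |
| 180 days | 56.4% | 105 days |

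**Effect of the cap in one case.** First dose 15 Oct 2019, true onset 10 Feb 2020, recorded as 2020:

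- ongoing: imputed 1 Oct 2020, 234 days late;
- ended 20 Jun 2020: imputed 1 Jun 2020, 112 days late;
- ended 20 Feb 2020: imputed 1 Feb 2020, not late.

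**On-treatment summary.** First dose 15 Nov 2018, last dose 1 Mar 2019, an ongoing adverse event that began in February 2019 and is recorded as 2019. The window closes on 31 Mar 2019. The imputed onset is 1 Nov 2019, 245 days after last dose, so the event drops out. As an illustration, with discontinuation uniform over Weeks 4 to 108 and no end date, about 21% of later-year on-treatment events would be re-dated beyond the window.

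**Immunosuppression sensitivity analysis.** Another patient, also first dosed 15 Nov 2018 and still on treatment, starts a steroid on 1 Feb 2019. It is recorded as 2019 and is either ongoing or stopped after 2019. The imputed start is 1 Nov 2019. Target dates are 7 Feb (Week 12), 2 May (Week 24), 25 Jul (Week 36) and 17 Oct 2019 (Week 48). All four values follow the true start and all four are kept.

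**With January.** 1 January of the onset year cannot be after the true onset, so the late share becomes 0%.

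**The case against.** **The current rule is centred.** Under uniform months it is late in 66 of 144 pairs, right in 12 and early in 66, so the mean month error is zero. January is early in 11 of 12 months, by 5.5 months on average. It could therefore remove eGFR values from before immunosuppressant initiation, or count a few off-treatment events as on-treatment. This stands as a cost. It does not rescue item 2: items 1 and 3 also aim for the earliest on-study date, and both uses are better served by an early error than a late one.

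**The cap protects most short events.** This stands; a reader might infer that about half of all missing-month items are late, and the table shows otherwise. SAP 6.6.4 also gives a non-ongoing item with unknown end date the last contact date. If that date feeds item 2, which the SAP does not say, it caps the onset when it falls in the onset year. Ongoing items stay exposed.

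**The reach is narrow.** This stands. SAP 10 uses on-study data unless noted, and for completers SAP 10.1.3 counts every treatment-emergent event before open-label dosing as on-treatment. Only early discontinuers in selected summaries can change. Events are reviewed at each visit and incomplete entries are queried (Protocol 10.1, 13.4.2), so affected records should be few.

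**Double-blind versus open-label.** A reader might infer that late dating moves double-blind events into the extension. The documents do not support this as a material harm. Open-label dosing follows Week 112, about 784 − 730 = 54 days after the second anniversary of first dose. For 312 of 365 first-dose dates it begins in the second calendar year after first dose, and the first of the first-dose month in that year comes before it. Enumerating onsets in the year the extension starts, with no cap, about 1% of items are true double-blind events moved into the extension. The opposite error is about 37% now and about 50% with January. Final open-label analyses are left to a separate SAP.

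**Conclusion.** The defect holds in a limited form. For onset years after the first-dose year, item 2 uses an uninformative month, and items that are ongoing or end in a later year have no effective cap. About 46% of these are dated late in the first calendar year after first dose. That figure rests on uniform, independent months and ranges from 0% to 92% by first-dose month. Individual dates can be wrong by many months, or impossible if they follow last contact or death.

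Two further readings are not supported. Treatment-emergent status does not change: any date in a later year is after first dose, and SAP 10.1 counts undetermined events as treatment-emergent. The primary slope models do not use these dates.

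What is affected is the on-treatment summaries for early discontinuers (10.1.3), the analyses excluding eGFR after immunosuppressant initiation or intensification (8.5.2, 8.7), and the days-on and time-to-first-use analyses (8.8.9). The number of affected records is not in the documents. This is a minor point, worth correcting because it is cheap.

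**What to change.** Amend item 2 of SAP 6.6.3. If the onset year equals the first-dose year, keep the present rule. If it is later, use January, or the month of the end date if that is earlier. Add that no imputed onset may fall after the end date, last contact or death, and state whether an end date imputed under 6.6.4 counts for this limit.

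The cost is one or two sentences and a small programming change, made before unblinding. The analytic cost is the early dating described above. A listing of records with an imputed onset month would show how many there are and whether the choice matters.

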6.6.4. Missing Adverse Event or Concomitant Medication End Date

If the entire end date is unknown and the event or medication is not considered ongoing at the end of study or follow-up, the event will be assumed to have ended on the last date of contact for the patient.

If only the day of end date is unknown, the day will be assumed to be the last of the month or the last date of contact for the patient, whichever is earlier.

If both the day and month of end date are unknown, the event will be assumed to have ended on the last day of the year or the last date of contact for the patient, whichever is earlier.

6.6.5. Missing Adverse Event Severity or Relationship

An event with missing severity will be considered severe. An event with missing relationship will be considered related to study medication.

7. STUDY POPULATION

7.1. Patient Disposition

Patient disposition will be tabulated by treatment group and overall and will include the number of patients who screened, failed screening, enrolled/randomized, received study medication, completed double-blind treatment, discontinued study medication (including reasons), completed the double-blind period, and discontinued the study during the double-blind period (including reasons). At the interim analysis, the number of patients who enrolled in the OLE period, discontinued sparsentan in the OLE period (including reasons) and discontinued the study during the OLE period will also be tabulated.

The number and percentage of patients in each analysis set will be summarized.

Patient enrollment by study site and country will be tabulated by treatment group and overall.

A by-patient listing of inclusion into analysis sets and study completion information including reason for study drug discontinuation or early withdrawal from study, if applicable, will be presented.

7.2. Screen Failures

The reason for screen failures will be summarized by region or site, as appropriate.

7.3. Protocol Deviations

Protocol deviations for missed visits, missed assessments, out of window visits or assessments, and violations of inclusion/exclusion criteria (where possible) will be determined based on available data. All other protocol deviations will be collected through study monitoring.

Protocol deviations that could potentially affect the efficacy or safety conclusions of the study will be identified and the assessment of determination of evaluable patients for analysis populations (PP Analysis Set and PK Analysis) will be performed and approved by the Study Statistician, Medical Monitor, and Clinical Study Manager prior to database lock and unblinding of individual patient treatment information.

Evaluability of patients will be based on the following:

- Compliance of study entry criteria (inclusion and exclusion)
- Correct stratification at randomization
- Received the randomized treatment
- Adequate study medication exposure (no extended dosing interruptions)
- Adequate treatment compliance based on prescribed dose level (within 80% to 120%)
- No prohibited concomitant medications or therapies during the study
- No accidental or intentional unblinding at the investigational site

- No other major protocol deviations that may affect efficacy or safety conclusions, may include:
 - Non-withdrawal although at least 1 withdrawal criterion was met
 - Extensive visit window violations
 - Extensive missing visits
 - Non-adherence to study procedures
 - Inadequate handling of study medication

Major protocol deviations will be summarized by deviation category (overall and due to coronavirus disease 2019 [COVID-19]) and presented in a by-patient data listing.

7.4. Demographic and Baseline Characteristics

Demographic variables will include the following:

- Age at informed consent
- Sex
- Race
- Ethnicity
- Geographic region and country

Other baseline characteristics will include the following:

- Weight (kg)
- Height (cm)
- Body mass index (BMI) (kg/m^2)
- Childbearing potential (for females only)
- Hemoglobin A1c (HbA1c)
- Baseline eGFR ($\text{mL}/\text{min}/1.73 \text{ m}^2$), including the following categories:
 - $<30 \text{ mL}/\text{min}/1.73 \text{ m}^2, \geq 30 \text{ to } <60 \text{ mL}/\text{min}/1.73 \text{ m}^2, \geq 60 \text{ mL}/\text{min}/1.73 \text{ m}^2$
 - $<30 \text{ mL}/\text{min}/1.73 \text{ m}^2, \geq 30 \text{ to } <45 \text{ mL}/\text{min}/1.73 \text{ m}^2, \geq 45 \text{ to } <60 \text{ mL}/\text{min}/1.73 \text{ m}^2, \geq 60 \text{ to } <90 \text{ mL}/\text{min}/1.73 \text{ m}^2, \geq 90 \text{ mL}/\text{min}/1.73 \text{ m}^2$
- Baseline UP/C (g/g), including the following categories:
 - Adults: $\leq 3.5 \text{ g}/\text{g}, >3.5 \text{ g}/\text{g}$; Pediatrics: $\leq 2 \text{ g}/\text{g}, >2 \text{ g}/\text{g}$
- Pretreatment medication use
 - Immunosuppressive agents (ie, steroids, calcineurin inhibitors [CNIs], mycophenolate mofetil [MMF], and other immunosuppressive agents including azathioprine and adrenocorticotrophic hormone [ACTH]) and RAAS inhibitors (ie, angiotensin converting enzyme [ACE] inhibitors, angiotensin receptor blockers, aldosterone blockers, and aliskiren)

- Baseline concomitant medication use
 - Antihypertensive medications, lipid-lowering medications, diuretics, immunosuppressive agents (steroids, CNIs, MMF, azathioprine, ACTH)
- Documented history of nephrotic syndrome
 - A patient will be considered to have documented history of nephrotic syndrome if the term “Nephrotic syndrome” is present in medical history or if all of the following conditions are met at any visits prior to the first dose of randomized treatment:
 - UP/C >3.5 g/g (adults) or UP/C >2 g/g (pediatrics)
 - Serum albumin <3.0 g/dL
 - Abnormal edema from physical examination

Demographics and baseline characteristics will be summarized and presented by treatment group and overall for the FAS, IAS, and PP Analysis Set. Summaries by randomization stratum will also be presented. A by-patient listing will also be provided.

7.5. Baseline FSGS Information

Baseline FSGS information will be summarized using data collected from the Medical History and FSGS Confirmation and Genetic Testing History eCRFs. The following variables will be summarized:

- Age at FSGS diagnosis
- Age at FSGS diagnosis group (<18, ≥18)
- Duration from FSGS diagnosis in years at time of informed consent
- Years since FSGS diagnosis (≤10, >10)
- Genetic testing available (Yes/No)
- FSGS-related genetic mutation

Baseline FSGS disease characteristics will be summarized and presented by treatment group and overall for the FAS, IAS, and PP Analysis Sets. Summaries by randomization stratum will also be presented. A by-patient listing will also be provided.

7.6. Medical History

Verbatim terms on eCRFs will be mapped to preferred terms (PTs) and system organ classes (SOCs) using Medical Dictionary for Regulatory Activities (MedDRA).

Medical history will be summarized by system organ class, preferred term, and treatment group using the safety population. Summaries will be ordered by descending order of incidence of system organ class and preferred term within each system organ class. A by-patient listing will also be provided.

7.7. Blinded Assessment of Comparability to Previous Study Populations

A statistical modeling exercise was conducted to support the design of this Phase 3 study. The modeling was performed using data from NEPTUNE, FSGS-CT, and DUET. The patient population included in the modeling was selected from these data sources to reflect the target patient population in DUPLEX. The modeling results ([Statistical Analysis Plan Modeling Report \[FSGS\], v1.0](#)) indicate that there is a relationship between eGFR slope and FPRE status across data sources. The exercise resulted in a model that reasonably predicts treatment difference in eGFR slopes given a treatment difference in FPRE response proportion, adjusting for potential prognostic factors. This relationship is key in establishing the utility of FPRE as a likely surrogate for early assessment of efficacy.

The applicability of the modeling results to the DUPLEX study lies in the comparability of the patient populations used in the modeling with that of the DUPLEX population. While it is reasonable to expect comparability due to the manner in which patients were selected for inclusion in the modeling, an assessment of population comparability is planned when approximately 190 patients have been randomized and while the study is still completely blinded. These 190 randomized patients constitute the same patient population used in the sensitivity analysis of the surrogate endpoint at the time of interim analysis described in [Section 6.6.2.2](#).

The comparability assessment will focus on baseline and demographic characteristics explored as potential prognostic factors in the previous modeling exercise. Continuous variables (ie, age, log UP/C, and eGFR) will be compared using t-tests. Categorical variables (ie, sex, race, and eGFR \leq or >120 mL/min/1.73m²) will be compared using chi-square tests. The specified baseline and demographic characteristics from DUPLEX will be compared against the corresponding variables from each of the following analysis datasets: NEPTUNE, FSGS-CT, DUET, pooled NEPTUNE + FSGS-CT, pooled DUET + NEPTUNE, and pooled NEPTUNE + FSGS-CT + DUET. Comparability of the DUPLEX population with a specific analysis dataset will be concluded if the null hypotheses of no difference for any of the 6 variables are not rejected at 2-sided $\alpha = 0.05$ following the Benjamini-Hochberg procedure to control the family-wise error rate.

If comparability cannot be concluded, the previous modeling exercise will be replicated on a subset of patients from the previous studies that match those from DUPLEX. Matching will be based on propensity scores. Results of the comparability assessment and the revised modeling, as applicable, will be communicated to the Food and Drug Administration prior to performing the planned unblinded interim analysis.

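### SAP 7.7 takes non-rejection of six difference tests as comparability, with no tolerable difference stated, and makes the propensity-matched re-fit depend on that result

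*SAP*

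**What the plan says.** SAP 7.7 rests the use of the historical model, which links the FSGS partial remission endpoint (FPRE) to eGFR slope, on DUPLEX patients resembling those used to build it. To check this, "an assessment of population comparability is planned when approximately 190 patients have been randomized", while the study is still blinded.

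- **Tests.** "Continuous variables (ie, age, log UP/C, and eGFR) will be compared using t-tests"; sex, race and eGFR split at 120 "will be compared using chi-square tests".
- **Comparators.** Six datasets: "NEPTUNE, FSGS-CT, DUET, pooled NEPTUNE + FSGS-CT, pooled DUET + NEPTUNE, and pooled NEPTUNE + FSGS-CT + DUET".
- **Rule.** Comparability with a dataset "will be concluded if the null hypotheses of no difference for any of the 6 variables are not rejected" at two-sided 0.05, "following the Benjamini-Hochberg procedure to control the family-wise error rate". Read literally, the word *any* is ambiguous. The sensible reading, used here, is that none of the six is rejected.
- **Consequence.** "If comparability cannot be concluded, the previous modeling exercise will be replicated on a subset of patients" of the earlier studies, chosen by propensity score to match DUPLEX.

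The comparability results, and the revised modelling if there is any, go to the FDA before the unblinded interim. The section gives no margin, effect-size limit, confidence interval or power for the assessment. It does not say which of the six verdicts governs if they disagree.

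**The concern.** A difference test that fails to reject shows only that the data did not establish a difference. Without a stated tolerable difference and enough patients to exclude it, similarity has not been shown.

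The multiplicity correction also acts in the unhelpful direction. The harmful error here is passing a population that really differs, and a correction that makes rejection harder makes that error more frequent.

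What depends on it is the support for FPRE as a likely surrogate. The same modelling supplied the responder versus non-responder slope difference of 8.4 mL/min/1.73 m² per year, and from it the projected chronic-slope effect (8.4 × 0.30 = 2.52) in SAP 4.3.1.2. The matched re-fit is the planned safeguard, and a false pass leaves it undone.

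**Working it through.** **Inputs.** DUPLEX n = 190, six tests and two-sided 0.05 come from SAP 7.7. DUET enrolment of 109 comes from Protocol Section 4; it is an upper bound, because SAP 7.7 says the modelling patients were selected. The NEPTUNE, FSGS-CT and pooled sizes are not in the documents, so 60 and 400 are assumptions to show a range. Further assumptions are six independent tests and normal two-sample statistics with differences in SD units.

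**1. The stated error rate.** Benjamini-Hochberg compares the ordered p-values with 0.05 × i/6, that is 0.0083, 0.0167, 0.025, 0.033, 0.042 and 0.05. Simulation with one million draws per case gives the chance of at least one false rejection:

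| Variables that clearly differ | 0 | 1 | 2 | 3 | 4 | 5 |
|---|---|---|---|---|---|---|
| Family-wise error | 5.0% | 8% | 9.7% | 9.7% | 8% | 5.0% |

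The stated 0.05 is reproduced when no variable differs. It does not hold in general.

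**2. Chance of passing, 190 versus 109, one variable off by 0.3 SD.**

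- SE = √(1/190 + 1/109) = 0.1202; shift = 0.3/0.1202 = 2.497.
- Unadjusted (critical value 1.960): the differing variable escapes rejection with probability 0.296. The other five all escape with probability 0.95⁵ = 0.774. Product: 0.229, or **23%**.
- Bonferroni (critical value 2.638 for 0.05/6): 0.556 × (1 − 0.0083)⁵ = 0.556 × 0.959 = 0.534.
- Benjamini-Hochberg rejects slightly more often than Bonferroni. Simulation gives 0.529, or **53%**.

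For reference, identical populations pass 95% of the time with the correction and 0.95⁶ = 73.5% without it.

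**3. Pass rates under the SAP rule, one variable differing.**

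| Comparator patients | 0.2 SD | 0.3 SD | 0.5 SD |
|---|---|---|---|
| 60 (assumed) | 86% | 70% | 22% |
| 109 (DUET enrolment) | 80% | 53% | 6% |
| 400 (assumed) | 61% | 21% | 0.1% |

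**4. What the rule can detect.** With 109 comparators, the difference found with 80% power in one variable is (2.638 + 0.842) × 0.1202 = 0.42 SD.

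**The case against.** The case on the other side is substantial, and most of it stands as a limit on how far the point goes.

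- **The mislabel.** A reader might infer that choosing Benjamini-Hochberg over a true family-wise method causes the false passes. It does not. The decision is global, and its error is 0.05 when all six nulls are true. The 9.7% arises only when two or three variables clearly differ, and comparability is then already refused. Bonferroni or Holm would pass slightly more often (53.4% against 52.9%).
- **Comparator size.** A reader might also infer that the verdict is decided mainly by a small comparator. The documents give a size only for DUET, and the true difference matters at least as much: at 109 comparators, passing falls from 80% at 0.2 SD to 6% at 0.5 SD. A large pool errs the other way; with an assumed 400, the rule rejects 39% of the time at 0.2 SD.
- **Dropping the correction.** This is no remedy, since identical populations would then fail about a quarter of the time.
- **Consequences.** The step is blinded, its results go to the FDA whichever way it falls, and it is not part of the testing hierarchy in SAP 8.4. FPRE and both slopes are tested directly on randomised data, and the historical model already adjusts for potential prognostic factors.
- **Independence.** eGFR enters twice, so the six tests are correlated, and the calculation does not model this.

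None of this supplies a tolerable difference or turns non-rejection into evidence of similarity. The probability that the re-fit is actually skipped cannot be computed, because the SAP does not say which dataset's verdict governs.

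**Conclusion.** The point holds for the decision rule. As written, the rule would declare DUPLEX comparable with a 109-patient DUET dataset about half the time (53%) when one variable differs by 0.3 SD, and four times in five (80%) at 0.2 SD. The correction accounts for much of this, since the unadjusted figure at 0.3 SD is 23%. Over an assumed 60 to 400 comparators, the 0.3 SD pass rate runs from about 70% to 21%. These figures rest on independent tests, a normal approximation and DUET's full enrolment being used.

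The consequence is that the matched re-fit supporting the FPRE-to-slope model may not be run before the interim. The documents do not support going further and saying that the trial's type I error or its FPRE and slope tests are compromised. The family-wise statement is wrong as written and should be corrected, but it is a separate wording error with no bearing on the pass/fail result.

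**What to change.** 1. Run and report the propensity-matched re-fit in every case, instead of only when the tests reject.
2. Report standardised differences with confidence intervals for the six variables against each dataset, as description and not as a pass/fail rule.
3. Delete the family-wise claim, or state that Benjamini-Hochberg controls the false discovery rate.

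Replacing the tests with a standardised-difference limit is not advised as the trigger, because it still depends on sample size. With a point-estimate limit of 0.25, identical populations pass all six variables (2Φ(0.25/SE) − 1)⁶ = 56%, 80% and 97% of the time with 60, 109 and 400 comparators. If instead the 90% interval must lie within ±0.25, identical populations with 109 comparators pass a single variable 34% of the time and all six about 0.1% of the time.

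The cost is one additional model fit, for which the SAP already provides, one table, and revised wording in SAP 7.7.
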